5.0 METHODOLOGY

5.1.1 Subject Inclusion Criteria

In order to be eligible for participation in this trial, the subject must:

1. Be willing and able to provide written informed consent/assent for the trial.
2. Be \geq 18 years of age on day of signing informed consent.
3. Have biopsy-proven residual disease. Measurable disease per RECIST 1.1 is not required. All measurements should be recorded in order to evaluate response..
4. Be willing to provide tissue from a newly obtained core biopsy of a tumor lesion. *Newly-obtained is defined as a specimen obtained up to 6 weeks (42 days) prior to initiation of treatment on Day 1 and following completion of RT/CRT. Tissue from fine needle aspirations (FNA) may be used if sufficient tissue is available.*
5. Have a performance status of 0 or 1 or 2 on the ECOG Performance Scale.

- Demonstrate adequate organ function as defined in Table 1. Labs value need to be assessed within 14 days of study treatment.

Table 1 Adequate Organ Function Laboratory Values

System	Laboratory Value
Hematological	
Absolute neutrophil count (ANC)	$\geq 1,500 / \mu\text{L}$
Platelets	$\geq 100,000 / \mu\text{L}$
Hemoglobin	$\geq 9 \text{ g/dL}$ or $\geq 5.6 \text{ mmol/L}$ without transfusion or EPO dependency (within 7 days of assessment)
Renal	
Serum creatinine OR Measured or calculated ^a creatinine clearance (GFR can also be used in place of creatinine or CrCl)	$\leq 1.5 \times$ upper limit of normal (ULN) OR $\geq 60 \text{ mL/min}$ for subject with creatinine levels $> 1.5 \times$ institutional ULN
Hepatic	
Serum total bilirubin	$\leq 1.5 \times$ ULN OR Direct bilirubin \leq ULN for subjects with total bilirubin levels $> 1.5 \text{ ULN}$
AST (SGOT) and ALT (SGPT)	$\leq 2.5 \times$ ULN
Albumin	$\geq 2.5 \text{ g/dL}$
Coagulation	
International Normalized Ratio (INR) or Prothrombin Time (PT)	$\leq 1.5 \times$ ULN unless subject is receiving anticoagulant therapy as long as PT or PTT is within therapeutic range of intended use of anticoagulants
Activated Partial Thromboplastin Time (aPTT)	$\leq 1.5 \times$ ULN unless subject is receiving anticoagulant therapy as long as PT or PTT is within therapeutic range of intended use of anticoagulants

^aCreatinine clearance should be calculated per institutional standard.

- Female subject of childbearing potential should have a negative urine or serum pregnancy within 72 hours prior to receiving the first dose of study medication. If the urine test is positive or cannot be confirmed as negative, a serum pregnancy test will be required.
- Female subjects of childbearing potential should be willing to use 2 methods of birth control or be surgically sterile, or abstain from heterosexual activity for the course of the study through 120 days after the last dose of study medication (Reference Section 5.7.2). Subjects of childbearing potential are those who have not been surgically sterilized or have not been free from menses for > 1 year.
- Male subjects should agree to use an adequate method of contraception starting with the first dose of study therapy through 120 days after the last dose of study therapy.
- Patients must have a history of Stage I-IVB SCC of the head and neck arising from the oral cavity, oropharynx, nasopharynx, larynx, or hypopharynx and must have been treated with definitive intent radiation (with or without systemic therapy)

11. Patients must be at least 6 weeks (42 days) and no more than 24 weeks (168 days) from completion of radiation with or without systemic therapy at the time of the biopsy confirming residual disease. Patients must receive the first dose of study medication no more than 28 weeks following completion of radiation.
12. Patients must have pathological evidence of persistent lymph node disease or persistent disease at the primary tumor site with viable tumor cells confirmed by a biopsy within 24 weeks of study treatment and no evidence of metastatic disease following primary radiation with or without systemic therapy confirmed by a CT scan within 4 weeks of study treatment. If a biopsy confirming residual disease has not been performed, this can be performed after obtaining consent, during the screening procedures.
13. Persistent lymph node disease with viable tumor cells will be determined by the histological determination of tumor viability.
14. All persistent disease must have received at least 66 Gy in 1.8-2Gy fractions of radiotherapy to the area of residual disease (or a biologically equivalent dose given by the linear quadratic equation: biologically equivalent dose (BED) = $nd(1 + d/(a/\beta))$, where **n** is the number of fractions, **d** dose per fraction and the **a/β** ratio for tumor is 10. Previous radiation records will be obtained to confirm adequate dosing.

5.1.2 Subject Exclusion Criteria

The subject must be excluded from participating in the trial if the subject:

1. Is currently participating and receiving study therapy or has participated in a study of an investigational agent and received study therapy or used an investigational device within 4 weeks of the first dose of treatment.
2. Has a diagnosis of immunodeficiency or is receiving supraphysiologic doses of systemic steroid therapy or any other form of immunosuppressive therapy within 7 days prior to the first dose of trial treatment. A physiologic dose of steroids is defined as up to 10mg of prednisone daily (or its equivalent).
3. Has a known history of active TB (Bacillus Tuberculosis)
4. Hypersensitivity to pembrolizumab or any of its excipients.
5. Has had a prior anti-cancer monoclonal antibody (mAb) within 4 weeks prior to study Day 1 or who has not recovered (i.e., \leq Grade 1 or at baseline) from acute, non-hematological adverse events due to agents administered more than 4 weeks earlier unless otherwise approved by the Principal Investigator.
 - Note: Subjects with \leq Grade 2 neuropathy, any grade dysphagia, \leq Grade 2 pain, \leq Grade 2 weight loss, any grade hyperpigmentation of skin, any grade fatigue, any grade xerostomia, and any grade dysgeusia, are an exception to this

criterion and may qualify for the study. Also please note that the presence of a feeding tube to aid with nutrition does not disqualify patients from study.

- Note: If subject received major surgery, they must have recovered adequately from the toxicity and/or complications from the intervention prior to starting therapy.
- 6. Has had prior chemotherapy, targeted small molecule therapy, or radiation therapy within 2 weeks prior to the first protocol treatment or who has not recovered (i.e., \leq Grade 1 or at baseline) from acute, non-hematological adverse events due to a previously administered agent unless otherwise approved by the Principal Investigator.
 - Note: Subjects with \leq Grade 2 neuropathy, any grade dysphagia, \leq Grade 2 pain, \leq Grade 2 weight loss, any grade hyperpigmentation of skin, any grade fatigue, any grade xerostomia, and any grade dysgeusia, are an exception to this criterion and may qualify for the study. Also please note that the presence of a feeding tube to aid with nutrition does not disqualify patients from study.
 - Note: If subject received major surgery, they must have recovered adequately from the toxicity and/or complications from the intervention prior to starting therapy.
- 7. Has a known additional malignancy that is progressing or requires active treatment. Exceptions include basal cell carcinoma of the skin or squamous cell carcinoma of the skin that has undergone potentially curative therapy or in situ cervical cancer.
- 8. Has known active central nervous system (CNS) metastases and/or carcinomatous meningitis. Subjects with previously treated brain metastases may participate provided they are stable (without evidence of progression by imaging for at least four weeks prior to the first dose of trial treatment and any neurologic symptoms have returned to baseline), have no evidence of new or enlarging brain metastases, and are not using steroids for at least 7 days prior to trial treatment. This exception does not include carcinomatous meningitis which is excluded regardless of clinical stability.
- 9. Has active autoimmune disease that has required systemic treatment in the past 2 years (i.e. with use of disease modifying agents, corticosteroids or immunosuppressive drugs). Replacement therapy (eg., thyroxine, insulin, or physiologic corticosteroid replacement therapy for adrenal or pituitary insufficiency, etc.) is not considered a form of systemic treatment.
- 10. Has known history of non-infectious pneumonitis that required steroids, or current pneumonitis.
- 11. Has an active infection requiring systemic therapy.
- 12. Has a history or current evidence of any condition, therapy, or laboratory abnormality that might confound the results of the trial, interfere with the subject's participation for

the full duration of the trial, or is not in the best interest of the subject to participate, in the opinion of the treating investigator.

13. Has known psychiatric or substance abuse disorders that would interfere with cooperation with the requirements of the trial.
14. Is pregnant or breastfeeding, or expecting to conceive or father children within the projected duration of the trial, starting with the pre-screening or screening visit through 120 days after the last dose of trial treatment.
15. Has received prior therapy with an anti-PD-1, anti-PD-L1, or anti-PD-L2 agent.
16. Has a known history of Human Immunodeficiency Virus (HIV) (HIV 1/2 antibodies).
17. Has known active Hepatitis B (e.g., HBsAg reactive) or Hepatitis C (e.g., HCV RNA [qualitative] is detected).
18. Has received a live vaccine within 30 days of the first protocol treatment.

Note: Seasonal influenza vaccines for injection are generally inactivated flu vaccines and are allowed; however intranasal influenza vaccines (e.g., Flu-Mist®) are live attenuated vaccines, and are not allowed.

19. Any patient receiving adjuvant systemic therapy following the completion of radiation therapy is ineligible.
20. Any patient with evidence of distant metastatic disease on a CT within 4 weeks of treatment is ineligible.
21. Evidence of interstitial lung disease.

5.2 Trial Treatments

The treatment to be used in this trial is outlined below in Table 2

Table 2 Trial Treatment

Drug	Dose/Potency	Dose Frequency	Route of Administration	Regimen/Treatment Period	Use
Pembrolizumab	200 mg	Q3W	IV infusion	Day 1 of each 3 week cycle	Experimental

5.2.1 Dose Selection/Modification

5.2.1.1 Dose Selection

The rationale for selection of doses to be used in this trial is provided in Section 4.0 – Background and Rationale.

Details on preparation and administration of pembrolizumab (MK-3475) are provided in the Pharmacy Manual.

5.2.1.2 Dose Modification

Adverse events (both non-serious and serious) associated with pembrolizumab exposure may represent an immunologic etiology. These adverse events may occur shortly after the first dose or several months after the last dose of treatment. Pembrolizumab must be withheld for drug-related toxicities and severe or life-threatening AEs as per Table 3 below. See Section 5.6.1 for supportive care guidelines, including use of corticosteroids.

Table 3

Dose Modification Guidelines for Drug-Related Adverse Events

Toxicity	Hold Treatment For Grade	Timing for Restarting Treatment	Discontinue Subject
Diarrhea/Colitis	2-3	Toxicity resolves to Grade 0-1.	Toxicity does not resolve within 12 weeks of last dose or inability to reduce corticosteroid to 10 mg or less of prednisone or equivalent per day within 12 weeks.
	4	Permanently discontinue	Permanently discontinue
AST, ALT, or Increased Bilirubin	2	Toxicity resolves to Grade 0-1	Toxicity does not resolve within 12 weeks of last dose.
	3-4	Permanently discontinue (see exception below) ¹	Permanently discontinue
Type 1 diabetes mellitus (if new onset) or Hyperglycemia	T1DM or 3-4	Hold pembrolizumab for new onset Type 1 diabetes mellitus or Grade 3-4 hyperglycemia associated with evidence of beta cell failure.	Resume pembrolizumab when patients are clinically and metabolically stable.
Hypophysitis	2-3	Toxicity resolves to Grade 0-1	Toxicity does not resolve within 12 weeks of last dose or inability to reduce corticosteroid to 10 mg or less of prednisone or equivalent per day within 12 weeks.
	4	Permanently discontinue	Permanently discontinue
Hyperthyroidism	3	Toxicity resolves to Grade 0-1	Toxicity does not resolve within 12 weeks of last dose or inability to reduce corticosteroid to 10 mg or less of prednisone or equivalent per day within 12 weeks.
	4	Permanently discontinue	Permanently discontinue
Hypothyroidism	2-4	Therapy with pembrolizumab can be continued while treatment for the thyroid disorder is instituted	Therapy with pembrolizumab can be continued while treatment for the thyroid disorder is instituted.
Infusion Reaction	3-4	Permanently discontinue	Permanently discontinue
Pneumonitis	2	Toxicity resolves to Grade 0-1	Toxicity does not resolve within 12 weeks of last dose or inability to reduce corticosteroid to 10 mg or less of prednisone or equivalent per day within 12 weeks.

Toxicity	Hold Treatment For Grade	Timing for Restarting Treatment	Discontinue Subject
	3-4	Permanently discontinue	Permanently discontinue
Renal Failure or Nephritis	2	Toxicity resolves to Grade 0-1	Toxicity does not resolve within 12 weeks of last dose or inability to reduce corticosteroid to 10 mg or less of prednisone or equivalent per day within 12 weeks.
	3-4	Permanently discontinue	Permanently discontinue
All Other Drug-Related Toxicity ²	3 or Severe	Toxicity resolves to Grade 0-1	Toxicity does not resolve within 12 weeks of last dose or inability to reduce corticosteroid to 10 mg or less of prednisone or equivalent per day within 12 weeks.
	4	Permanently discontinue	Permanently discontinue

Note: Permanently discontinue for any severe or Grade 3 drug-related AE that recurs or any life-threatening event.

¹ For patients with liver metastasis who begin treatment with Grade 2 AST or ALT, if AST or ALT increases by greater than or equal to 50% relative to baseline and lasts for at least 1 week then patients should be discontinued.

² Patients with intolerable or persistent Grade 2 drug-related AE may hold study medication at physician discretion. Permanently discontinue study drug for persistent Grade 2 adverse reactions for which treatment with study drug has been held, that do not recover to Grade 0-1 within 12 weeks of the last dose.

Dosing interruptions are permitted in the case of medical / surgical events or logistical reasons not related to study therapy (e.g., elective surgery, unrelated medical events, patient vacation, and/or holidays). Subjects should be placed back on study therapy within 3 weeks of the scheduled interruption, unless otherwise discussed with the Sponsor. The reason for interruption should be documented in the patient's study record. Dosing may be interrupted for up to 6 weeks at the end of cycle 4 as protocol required assessments to determine treatment continuation are performed.

5.2.2 Timing of Dose Administration

Trial treatment should be administered on Day 1 of each cycle after all procedures/assessments have been completed as detailed on the Trial Flow Chart (Section 6.0). Trial treatment may be administered up to 3 days before or after the scheduled Day 1 of each cycle due to administrative reasons.

All trial treatments will be administered on an outpatient basis.

Pembrolizumab 200 mg will be administered as a 30 minute IV infusion every 3 weeks. Sites should make every effort to target infusion timing to be as close to 30 minutes as possible. However, given the variability of infusion pumps from site to site, a window of -5 minutes and +10 minutes is permitted (i.e., infusion time is 30 minutes: -5 min/+10 min).

The Pharmacy Manual contains specific instructions for the preparation of the pembrolizumab infusion fluid and administration of infusion solution.

5.2.3 Trial Blinding/Masking

This is an open-label trial; therefore, the Sponsor, investigator and subject will know the treatment administered.

5.3 Treatment Allocation

Patients with Stage I-IVB HNSCC of the larynx, hypopharynx, oropharynx, nasopharynx, or oral cavity) who have been treated with curative intent radiation, chemoradiation, or cetuximab and radiation within 6-24 weeks and have biopsy proven residual disease will be eligible for enrollment.

All patients upon biopsy confirmation of residual disease will have restaging scans (CT neck/chest/abdomen/pelvis). Patients will require evaluation by an ENT to determine whether their disease is considered resectable or unresectable. Patients will then receive pembrolizumab at a dose of 200mg Q3 weeks for 4 cycles. A CT scan of the neck/chest/abdomen/pelvis will be performed at the end of cycle 2 to check for progression of disease (irPD), defined using immune related response criteria. Patients with progression prior to four cycles of pembrolizumab will discontinue study therapy.

After four cycles patients will undergo repeat CT neck/chest/abdomen/pelvis and a biopsy. Patients will then be re-evaluated by otolaryngology to determine the current status of their local/locoregional disease and to determine whether it is technically resectable. At this time patients that are deemed resectable can go on to surgical resection, and those deemed unresectable or who refuse resection can continue on pembrolizumab until evidence of progression or for up to 1 year. These patients will not be evaluable for the study endpoints, although their response rates and overall survival will be reported. An early stopping rule exists, such that during enrollment of the first 10 patients considered resectable, at screening if 3 or more become unresectable during the study the trial will close. The plan is to enroll 24 patients.

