2.0 TRIAL DESIGN

2.1 Trial Design

[figure not shown]
This is a phase II study for patients with squamous cell carcinoma of the head and neck who have residual disease following definitive therapy with radiation (with or without systemic therapy). Patients must be diagnosed with biopsy-proven residual disease within 24 weeks of completion of radiation therapy with or without systemic therapy. Residual disease must be biopsy proven and can be either from lymph nodes in the neck, or from the primary tumor site. Prior to beginning study therapy patients are evaluated by an ENT to determine if they have disease amenable to surgical resection. Both resectable and unresectable patients will be eligible for participation in the study. Patients will have repeat scans after 4 cycles (12 weeks) of treatment or disease progression, whichever comes first. Scans after 2 cycles will be performed as clinically indicated.

Patients then receive four cycles of pembrolizumab at 200mg given every three weeks. Repeat imaging is performed after two cycles to ensure there is not progression of disease. Patients who were deemed resectable prior to being enrolled on the study who show clinical radiographic or clinical progression after two cycles of therapy will discontinue study drug and proceed to surgical resection. Patients deemed to have unresectable disease who have radiographic progression but have signs of clinical benefit can continue on the drug. Following completion of four cycles of therapy, a biopsy is performed, and patients are again evaluated by ENT surgery. Patients with disease considered amenable to surgery would go on to surgical

resection. Patients considered unresectable or who refuse surgery can continue pembrolizumab until time of progression or for 1 year.

The primary endpoint is the overall response rate. Secondary endpoints include change in PD-L1 expression from baseline, changes in key immune cells, and progression free survival.

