2.2 Trial Diagram

3.0 OBJECTIVE(S) & HYPOTHESIS(ES)

3.1 Primary Objective(s) & Hypothesis(es)

(1) **Objective:** To determine the overall response rate to pembrolizumab for patients with residual disease following radiation with or without systemic therapy for squamous cell carcinoma of the head and neck. The response rate is defined at the time of progression or the completion of four cycles of therapy, whichever is earlier.

Hypothesis: The use of pembrolizumab in patients with residual disease following radiation with or without systemic therapy will lead to an enhanced overall response rate due to treatment-related priming of the immune response.

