5.9 Subject Replacement Strategy

Patients will be replaced if they do not receive at least one cycle of pembrolizumab.

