6.2.2.12 Tumor Imaging and Assessment of Disease

CT neck, chest, abdomen and pelvis will be ordered at baseline and during the 3rd week of cycles 2, if clinically indicated, cycle 4 or at time of progression whichever comes first. Additional re-imaging may be obtained at the discretion of the investigator. For patients who are not amenable to resection following 4 cycles of therapy and who continue on pembrolizumab, a q8 week CT of the neck, chest, abdomen and pelvis will be obtained.

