6.2.2.12.2 Evaluation of Best Overall Response

The Best Overall Response is the best response recorded from the start of the treatment until completion of four cycles of study drug (taking as reference for progressive disease the smallest measurements recorded since the treatment started). For purpose of the primary endpoint of the study, the overall response will be measured during the post pembrolizumab, in comparison to the most immediate pre-pembrolizumab imaging.

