7.0 STATISTICAL ANALYSIS PLAN

7.1 Statistical Analysis Plan Summary

The primary objective of this phase II study is to determine the overall response rate in patients with squamous cell carcinoma of the head and neck who have residual disease following definitive radiation with or without systemic therapy. This will be a single arm study of 24 patients with Stage I-IVB HNSCC who have residual disease after being treated with definitive radiation with or without systemic therapy.

The expected rate of resolution of disease without any further therapy is thought to be approximately 10%. This is derived from the Princess Margaret Hospital experience of 493 patients undergoing definitive chemoradiation for head and neck SCC, approximately 50% had less than a complete response to chemoradiation therapy at 8-12 week post therapy assessment²⁶. An additional 33% achieved CR between weeks 12 and 24. Of patients taken to neck dissection with less than a complete response (CR) the rate of positive residual tumor cells within the neck was 35%. This is substantially higher than the rate of positive residual cells at neck dissection in patients who achieve a CR to initial therapy, which was 9%. Thus it is estimated, that approximately 10% of patients that would likely have had pathologic residual disease at the 8-12 week assessment will achieve pathologic CR by 24 weeks without any further intervention. This estimate is given by:

the percentage of patients achieving a CR between weeks 12 and 24 x (the rate of pathologic positivity in non CR patients – the rate of pathologic positivity in CR patients)

$$= 33\% \times (35\% - 9\%) = 8.7\%, \text{ or approximately } 10\%.$$

Thus, assuming a baseline response rate of 10% (based on the Princess Margaret experience discussed above) and an improvement in response rate to 27% after treatment of chemoradiation, we will have 81% power to detect this difference with 24 patients by exact one-sample binomial test at one-sided significance level of 0.10. If 27% or more of patients in the study develop a partial or complete response to pembrolizumab, this strategy will be deemed worth of further investigation.

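### Section 5.3 makes patients who continue pembrolizumab after cycle 4 non-evaluable, which contradicts the 24-patient primary analysis in Section 7.1 and selects patients on a status judged after treatment

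*Combined protocol and SAP*

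**What the plan says.** Section 5.3 (Treatment Allocation) describes the decision after four cycles, once CT, biopsy and ENT re-evaluation are done. Resectable patients can go to surgery; "those deemed unresectable or who refuse resection can continue on pembrolizumab until evidence of progression or for up to 1 year". The next sentence is: "These patients will not be evaluable for the study endpoints, although their response rates and overall survival will be reported".

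Other sections bear on who counts:

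- Section 2.1: "Both resectable and unresectable patients will be eligible for participation in the study".
- Section 3.1: "The response rate is defined at the time of progression or the completion of four cycles of therapy, whichever is earlier".
- Section 6.2.2.12.2: "The Best Overall Response is the best response recorded from the start of the treatment until completion of four cycles of study drug".
- Section 6.2.2.12, on imaging: "For patients who are not amenable to resection following 4 cycles of therapy and who continue on pembrolizumab, a q8 week CT" of neck, chest, abdomen and pelvis will be obtained.
- Section 5.9: "Patients will be replaced if they do not receive at least one cycle of pembrolizumab".
- Section 7.1: "we will have 81% power to detect this difference with 24 patients by exact one-sample binomial test", one-sided 0.10, for 10% against 27%. The criterion for further investigation is a proportion of the patients in the study. Section 7.1 does not repeat the exclusion and names no evaluable set.

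**The concern.** The nearest antecedent of the exclusion is the group continuing pembrolizumab after cycle 4. Membership of that group is settled after the cycle-4 CT and biopsy, in an open-label trial, when each patient's response is known. Dropping the group conditions the primary analysis on a post-treatment status that response can influence.

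Two analysts could use different denominators for the primary endpoint and both cite the protocol. On the literal reading fewer than 24 patients count and none of those lost is replaced. The direction of bias cannot be predicted, because the group mixes unresectable patients with patients who refuse surgery, and some of the latter may have refused because they responded. The exclusion refers to the study endpoints in the plural, so it would also reach PFS, which would then rest only on patients who had surgery after cycle 4 or had stopped by then.

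Two other readings are possible. (a) Only responses first seen after cycle 4 do not count; this fits Sections 3.1 and 6.2.2.12.2 and does no harm. (b) The sentence refers back to patients who progressed before four cycles; excluding them would remove non-responders directly.

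**Working it through.** **Inputs.** From Section 7.1: n = 24, null rate 10%, alternative 27%, exact one-sample binomial test, one-sided alpha 0.10. The number excluded and its relation to response are not in the documents, so every exclusion share below is an assumption.

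**Step 1: reproduce the plan's figure.** The critical value c is the smallest integer with P(X ≥ c | n, 0.10) ≤ 0.10; power is P(X ≥ c | n, 0.27). At n = 24, c = 4 gives alpha 0.214 (too large). c = 5 gives alpha 0.085 and power 0.817. The stated 81% is right, and it needs all 24 patients in the denominator.

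**Step 2: fewer evaluable patients, exclusion unrelated to response.** Same rule at smaller n:

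| Evaluable n | c | Actual alpha | Power at 27% |
|---|---|---|---|
| 24 | 5 | 0.085 | 81.7% |
| 23 | 5 | 0.073 | 78.5% |
| 22 | 5 | 0.062 | 75% |
| 20 | 5 | 0.043 | 66% |
| 18 | 4 | 0.098 | 76% |
| 16 | 4 | 0.068 | 66% |
| 14 | 4 | 0.044 | 55% |
| 12 | 4 | 0.026 | 41% |

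Power is not monotone in n because the test is discrete. For every n from 8 to 23 it is below 81%; the highest value is 78.5%, at n = 23. The number excluded would itself be random. With evaluable n ~ Bin(24, 1 − f) and c recomputed for each n, average power is 73% for f = 0.10, 68% for f = 0.25 and 51% for f = 0.50.

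**Step 3: exclusion related to response.** Let a and b be the fractions excluded among responders and non-responders, and p the true rate. The probability of being kept is k = p(1 − a) + (1 − p)(1 − b). The rate among those kept is q = p(1 − a)/k. Evaluable n ~ Bin(24, k), responses ~ Bin(n, q), and the rejection probability is summed over n. Example with p = 0.27, a = 0.40, b = 0.20: k = 0.27 × 0.60 + 0.73 × 0.80 = 0.746, and q = 0.162/0.746 = 0.217.

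| True p | a / b | Dropped | Apparent rate | P(reject) |
|---|---|---|---|---|
| 27% | 20% / 10% | 13% | 24.7% | power 63% |
| 27% | 40% / 20% | 25% | 21.7% | power 47% |
| 27% | 70% / 45% | 52% | 16.8% | power 20% |
| 10% | 10% / 20% | 19% | 11.1% | type I error 8.3% |
| 10% | 10% / 30% | 28% | 12.5% | type I error about 12.5% |
| 10% | 30% / 55% | 52.5% | 14.7% | type I error 14% |
| 10% | 20% / 60% | 56% | 18.2% | type I error 22% |

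**Step 4: the other readings.** Reading (a) changes nothing: n = 24, power 81.7%. Reading (b), with 25% of non-responders and no responders excluded: k = 0.10 + 0.90 × 0.75 = 0.775, q = 0.10/0.775 = 12.9%, type I error 13.5%.

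**The case against.** The strongest reply is that the authors meant reading (a). The sentence itself promises to report these patients' response rates and overall survival, so nothing is hidden and a reader could rebuild the 24-patient result. Section 7 is the analysis plan, it counts all 24, and a remark in a treatment-allocation paragraph should not override it.

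Part of this stands. Reading (a) is plausible and harmless, and the data would not be lost. But the sentence excludes patients, not later assessments, and it sets the reporting apart from the endpoints, so reporting does not put these patients into the primary test. No section says which text governs, and Section 7.1 defines no analysis set that would settle it.

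Other fair points limit the finding without removing it. Sections 2.1, 5.9 and 6.2.2.12 concern eligibility, replacement and data collection; they are in tension with the exclusion but do not strictly contradict it. The direct conflict is between 5.3 and 7.1, with 3.1 and 6.2.2.12.2 showing that the response is already observed. Unresectability after cycle 4 is a status that may correlate with response, not the outcome itself, and for patients unresectable at screening it may largely reflect baseline. That refusers tend to be responders is a possibility the documents do not support. Finally, the size is assumed throughout: in one modest case type I error stays below 0.10, and errors of 14% to 22% on the literal reading need about half the patients dropped.

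**Conclusion.** The concern holds. The protocol gives two incompatible denominators for its primary endpoint. Following Section 5.3 as written invalidates the 81% power claim for any loss within the range examined (1 to 16 patients) and leaves the nominal 0.10 unprotected once exclusion depends on response. With a rejection boundary of 5 responses in 24, one or two patients can change the conclusion, so this must be corrected before analysis.

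The contradiction and the 81.7% rest on the documents alone. The loss of power and the bias rest on assumed exclusion shares and could be small. Confidence is medium because the authors' intent is uncertain; under reading (a) only the wording is at fault.

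**What to change.** Replace the sentence in Section 5.3 and state the analysis set in Section 7.1, for example:

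> All patients who receive at least one cycle of pembrolizumab (as in Section 5.9) are included in the primary response analysis and in PFS and OS, whatever their resectability or surgery after cycle 4. Response is taken at progression or completion of four cycles, whichever is earlier. Responses first documented after the end-of-cycle-4 assessment are reported separately and do not count toward the primary endpoint. Treated patients with no post-baseline assessment count as non-responders.

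Two details belong in the same edit. The end-of-cycle-4 assessment should be defined to cover the post-treatment biopsy or PET that Section 6.2.2.12.1 uses for small lesions, given that Section 5.2.1.2 allows up to 6 weeks for the cycle-4 assessments. Sections 3.1 (response at a time point) and 6.2.2.12.2 (best response up to that point) should be worded alike.

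The cost is wording only: no extra patients or procedures, and no change to clinical management. The one downside is that the observed response rate may be slightly lower, because treated patients without an assessment count as non-responders.
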